A futility assessment will be triggered when 15 patients across all strata or 8 patients in a single stratum reach 24 weeks of treatment, whichever occurs first. If both criteria are met at the same time, the overall futility assessment will be performed.

The futility criterion is defined as follows:

- All strata (n=15): ≤3 responses meeting HI-E criteria, sustained from Week 16 to Week 24
- Single stratum (n=8): 0 (zero) responses

If either the overall or single stratum futility criterion is met, enrollment may discontinue for futility or further enrollment restricted to specific subsets of patients based on prior transfusion history may be considered. If neither criterion is met, enrollment will continue until a total of 45 response-evaluable patients are available at Week 24.

Enrollment will not pause during assessment periods unless futility analysis suggests clinical need to pause.

Patients will be enrolled into a 48-week treatment period, followed by a 28-day off-drug period. A safety follow-up visit occurs at the End of the Study (W52D1).

Patients demonstrating clinical benefit at the end of the planned 48-week treatment period may be offered the opportunity to remain on treatment and enter the Optional Prolonged treatment period. Patients who enter the Optional Prolonged treatment period will follow the Schedule of Events outlined in Table 1-2. Patients who permanently discontinue treatment during the Optional Prolonged treatment period should attend a safety follow-up visit no sooner than 28 days after their last dose of etavopivat.

Novo Nordisk will perform ongoing safety surveillance. Safety surveillance activities encompass the regular periodic safety data review from clinical trials, literature surveillance and safety information derived from other sources.

If new safety signals are identified, these will be evaluated by the etavopivat internal safety committee.

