9.3 Sample Size Considerations

An overall sample size of N=45 will provide 87.3% power to detect an increase in the response rate for the HI-E criteria. Specifically, the assumed response rates are 40% for the etavopivat intervention and 20% otherwise (null-hypothesis comparator). One-sided testing, a significance level of 0.025, and the exact binomial distribution are used for the calculations.

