9.5 Futility Assessment and Decision Rules

A futility assessment threshold has been selected for this study once 15 patients overall or 8 patients in a single transfusion stratum have evaluable responses on the HI-E criteria at Week 24, whichever occurs first. If the overall futility assessment is performed and \leq 3 responses are observed, enrollment may discontinue for futility. If there are 4 or more responses at 24-weeks observed, enrollment will continue until a total of approximately 45 response evaluable patients are available at Week 24. If the stratum-specific futility assessment is performed and no responses are observed, further enrollment may be restricted to specific subsets of patients based on prior transfusion history.

Enrollment will not pause during assessment periods unless futility analysis suggests clinical need to pause.

Assuming the pooled response rate of 40% is met, the probability of incorrectly declaring futility with 15 evaluable patients is 0.0905. This is calculated using the binomial cumulative distribution function with parameters n=15, p=0.4, x=3.

The single stratum futility assessment allows for the possibility that response rates in a single stratum may be lower than 40%, but the pooled response rate after incorporating the other strata could still reach 40%. The per-stratum futility threshold is intended to terminate enrollment in a stratum where the true response rate can be expected to be <25%. Under a binomial distribution with parameters n=8 and p=0.25, the probability of observing x=0 successes is 0.10011.

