9.6.1 Analysis of Primary Efficacy Endpoint

The primary endpoint is the pooled incidence of the HI-E criteria of ≥ 8 weeks duration (across strata), and it will be summarized with frequencies and proportions. Specifically, the primary endpoint is assessed following 24 weeks of etavopivat treatment. During those 24 weeks, if there had been an 8-week interval (or longer) where one of the below 3 conditions was maintained/persistently held, then the incidence of the primary endpoint is fulfilled:

- NTD patients: $\geq 1.5 \text{ g/dL}$ increase in Hb from baseline
- LTB patients: absence of any transfusion
- HTB patients: reduction by $\geq 50\%$ of RBC units

Analysis of the pooled incidence will test the hypothesis:

 $H_0: 0.2 \le P_1$

 $H_1: 0.2 > P_1$

Where $P_0 = 0.20$ is the assumed null proportion and P_1 is the observed proportion for etavopivat treated patients. This will be tested using a one-sided binomial exact test at the significance level of 0.025 for accuracy.

Tabular summaries will also include the exploratory incidence and test for each of the separate strata.

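### The stated 87.3% power for N=45 is neither the exact binomial value (85.7%) nor the power with the plan's own futility look (81.0% if 3 or fewer of 15 always ends the trial)

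*Protocol*

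**What the plan says.** Protocol 9.3 gives the power claim: "An overall sample size of N=45 will provide 87.3% power to detect an increase in the response rate for the HI-E criteria". Its inputs are "the assumed response rates are 40% for the etavopivat intervention and 20% otherwise (null-hypothesis comparator"), with the method described as "One-sided testing, a significance level of 0.025, and the exact binomial distribution are used for the calculations". SAP 3.1 repeats the statement. Protocol 9.6.1 confirms the final test: "This will be tested using a one-sided binomial exact test at the significance level of 0.025 for accuracy".

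The futility look is described elsewhere. Protocol 4.1: "A futility assessment will be triggered when 15 patients across all strata or 8 patients in a single stratum reach 24 weeks of treatment", whichever comes first. Protocol 9.5: "If the overall futility assessment is performed and \leq 3 responses are observed, enrollment may discontinue for futility"; with 4 or more responses, enrollment goes on to about 45 evaluable patients. For a 40% response rate, 9.5 adds that "the probability of incorrectly declaring futility with 15 evaluable patients is 0.0905". SAP 3.11 and 3.11.1 carry the same rule and the same figure.

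Neither protocol 9.3 nor SAP 3.1 mentions the look, and no section combines the 0.0905 with the power.

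**The concern.** The power statement describes a trial that always reaches 45 evaluable patients. The decision rule describes one that may end after 15. Some of the trials stopped at 15 would have succeeded at 45, so a stop that is followed must lower the power. The amount can be calculated from the plan's own inputs.

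The printed figure also fails to match its stated method, even with no look. Both gaps run in the same direction and make the design appear more protective of an active drug than it is. Anyone weighing a low interim count, or a negative final result, would rely on this number.

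**Working it through.** **Inputs.** N = 45, null rate 0.20, alternative 0.40, one-sided 0.025, exact binomial (protocol 9.3 and 9.6.1). Overall futility boundary: 3 or fewer of 15 (protocol 4.1 and 9.5).

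**1. The printed figure.** The one-sample normal approximation is

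Φ[(0.40 − 0.20 − 1.96·√(0.20·0.80/45)) / √(0.40·0.60/45)] = Φ[(0.20 − 0.1169)/0.0730] = Φ(1.138) ≈ 0.8725.

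This agrees with 87.3%, so the printed value looks like a normal approximation. The documents do not say how it was obtained.

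**2. Exact single-stage power.** The critical value is the smallest c with P(X ≥ c | 45, 0.20) ≤ 0.025.

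| c | Type I error at 20% | Power at 40% |
|---|---|---|
| 14 | 0.0521 | 0.9164 |
| **15** | **0.02499** | **0.8570** |
| 16 | 0.0110 | 0.7751 |

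So c = 15 and exact power is 85.7%. No cut-off gives 87.3%. The gap to the printed value is 87.3 − 85.7 = 1.6 points.

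**3. The false-stop probability.** P(X ≤ 3 | 15, 0.40) = 0.0905, which matches protocol 9.5.

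**4. Power with the overall stop always followed.** Count a stop as a failure and treat an interim response as the same event as a final response. Then

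power(p) = Σ over x = 4 to 15 of P(Bin(15, p) = x) × P(Bin(30, p) ≥ 15 − x).

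- At p = 0.40: 0.8102.
- At p = 0.20: 0.0218, the type I error with the stop.

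**5. What the stop costs.** 0.8570 − 0.8102 = 0.0467 (from unrounded values), or 4.7 points. This is less than 9.05 points because about half of the stopped trials (0.0905 − 0.0467 = 0.0438) would have failed at 45 anyway. The chance of missing a true 40% rate rises from 100 − 85.7 = 14.3% to 100 − 81.0 = 19.0%, about one third more.

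**6. If the single-stratum look comes first.** Assume a common 40% rate and treat 0 of 8 as a full stop:

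Σ over x = 1 to 8 of P(Bin(8, 0.40) = x) × P(Bin(37, 0.40) ≥ 15 − x) = 0.848, or 84.8%.

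**7. If interim responses are a subset of final responses.** Protocol 4.1 asks that responses in the overall rule be sustained from Week 16 to Week 24. The documents give no rate for this, so the following is an assumption for illustration. If 95% of final responders qualify at the interim, step 4 gives 79.0%; at 90% it gives 76.3%.

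**The case against.** The strongest reply is that 81.0% is not the power of this trial, because the written rule is looser than the model.

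- **Discretion.** Enrollment may stop; it need not. Protocol 4.1 also allows continued enrollment restricted to some strata, and SAP 3.8 lets the remaining strata be enlarged to reach 45. Restricted continuation is neither a full stop nor no stop, and the figures above do not model it.
- **Trigger.** Eight patients in one stratum may come first, and then the 15-patient rule may not be the one applied.
- **Patients already enrolled.** Enrollment does not pause for the look, and nothing says that enrolled patients are dropped or that the final test is forfeited. If a stop left 35 or 40 patients enrolled (assumed numbers) and all were tested at 0.025, power would be 82.9% or 84.3%.
- **Disclosure and use.** The 0.0905 is printed with its derivation, so the risk is not hidden. SAP 1.1 says that the study terminated early and that the SAP supports an abbreviated report, so no planned analysis changes.

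These points stand. They make 81.0% conditional, and they make this a reporting correction and not a flaw in the test. They do not rescue 87.3%: with no stop at all, exact power is 85.7%, and every scenario calculated here is at or below that.

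Two stronger readings are tempting. A reader might infer that the futility look costs 6.3 points (87.3 to 81.0). It costs 4.7; the other 1.6 come from the non-exact calculation and would remain without any look. A reader might also infer that power must lie between 81.0% and 85.7%. That is not a bound. Protocol 4.1 requires a sustained response, while SAP 3.11 counts a Week 16 responder who relapses by Week 24. Under the stricter definition, power could fall below 81.0%, as step 7 illustrates.

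**Conclusion.** The point holds with its conditions attached. The printed 87.3% is not the exact binomial power that it claims to be; that value is 85.7%. It also leaves out the futility look. If the overall rule is always followed as a full stop, with interim and final responses defined identically and exactly 45 evaluable patients otherwise, power is 81.0% and type I error 0.022. The loss due to the stop is 4.7 points.

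The final test stays valid: type I error is at or below 0.025 with or without the stop. A reader might link the early termination to this rule, but the documents do not give futility as the reason, and nothing here depends on it.

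**What to change.** In protocol 9.3 and SAP 3.1, replace the 87.3% statement with:

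> *With exactly 45 evaluable patients, success requires at least 15 responders. Exact power at 40% is 85.7% (type I error 0.025) if the futility rule is not applied, and 81.0% (type I error 0.022) if 3 or fewer responders in the first 15 always stops the trial as a failure, assuming interim and final responses are defined identically.*

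The word *exactly* matters because protocol 9.5 and SAP 3.11 say approximately 45, and at 46 the critical value becomes 16.

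Three additions belong with it:

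1. State whether the futility rule is binding.
2. Note that if the single-stratum look comes first and 0 of 8 is a full stop, power is 84.8% under a common 40% rate.
3. Reconcile the interim response definition between protocol 4.1 (with protocol 1.1 and SAP 1.2.1) and SAP 3.11, and say that the 81.0% depends on it.

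The cost is a few sentences in each document and a less favourable stated power. Sample size and boundary stay as they are. Since the study has ended early, the abbreviated report should carry the corrected figures if it quotes the design power.

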9.4 General Statistical Considerations

Continuous variables will be summarized descriptively via number of patients, mean, standard deviation, minimum, median, and maximum. Categorical variables will be summarized as the number and percent of patients in each category. Data summaries will be performed using the nominal visit unless otherwise specified.

Unless otherwise specified, all testing will be 2-sided at the 0.05 level of significance.

All data collected on study in the eCRF will be included in data listings.

9.4.1 Multicenter Studies

Data collected will be analyzed as a whole. Exploratory analyses by individual study sites may be conducted as warranted.

9.4.2 Handling of Missing Data

For patient reported outcome data, missing data imputation will be based on published instrument specific methods.

Full details of how missing data will be handled will be described in the SAP.

9.5 Futility Assessment and Decision Rules

A futility assessment threshold has been selected for this study once 15 patients overall or 8 patients in a single transfusion stratum have evaluable responses on the HI-E criteria at Week 24, whichever occurs first. If the overall futility assessment is performed and \leq 3 responses are observed, enrollment may discontinue for futility. If there are 4 or more responses at 24-weeks observed, enrollment will continue until a total of approximately 45 response evaluable patients are available at Week 24. If the stratum-specific futility assessment is performed and no responses are observed, further enrollment may be restricted to specific subsets of patients based on prior transfusion history.

Enrollment will not pause during assessment periods unless futility analysis suggests clinical need to pause.

Assuming the pooled response rate of 40% is met, the probability of incorrectly declaring futility with 15 evaluable patients is 0.0905. This is calculated using the binomial cumulative distribution function with parameters n=15, p=0.4, x=3.

The single stratum futility assessment allows for the possibility that response rates in a single stratum may be lower than 40%, but the pooled response rate after incorporating the other strata could still reach 40%. The per-stratum futility threshold is intended to terminate enrollment in a stratum where the true response rate can be expected to be <25%. Under a binomial distribution with parameters n=8 and p=0.25, the probability of observing x=0 successes is 0.10011.

9.6 Analysis of Efficacy

The primary analysis of Efficacy will be performed using the Efficacy Evaluable Set. Sensitivity will be performed using the PPS.

9.6.1 Analysis of Primary Efficacy Endpoint

The primary endpoint is the pooled incidence of the HI-E criteria of ≥ 8 weeks duration (across strata), and it will be summarized with frequencies and proportions. Specifically, the primary endpoint is assessed following 24 weeks of etavopivat treatment. During those 24 weeks, if there had been an 8-week interval (or longer) where one of the below 3 conditions was maintained/persistently held, then the incidence of the primary endpoint is fulfilled:

- NTD patients: $\geq 1.5 \text{ g/dL}$ increase in Hb from baseline
- LTB patients: absence of any transfusion
- HTB patients: reduction by $\geq 50\%$ of RBC units

Analysis of the pooled incidence will test the hypothesis:

 $H_0: 0.2 \le P_1$

 $H_1: 0.2 > P_1$

Where $P_0 = 0.20$ is the assumed null proportion and P_1 is the observed proportion for etavopivat treated patients. This will be tested using a one-sided binomial exact test at the significance level of 0.025 for accuracy.

Tabular summaries will also include the exploratory incidence and test for each of the separate strata.

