3. GENERAL STATISTICAL METHODS

3.1. Sample Size Justification

An overall sample size of N=45 will provide 87.3% power to detect an increase in the response rate for the HI-E criteria. Specifically, the assumed response rates are 40% for the etavopivat intervention and 20% otherwise (null-hypothesis comparator). One-sided testing, a significance level of 0.025, and the exact binomial distribution are used for the calculations.

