3.2. General Methods

In general, tables will summarize data by transfusion history stratum at Day 1. All statistical analyses will be performed using SAS statistical software Version 9.4 or higher, unless otherwise noted. For categorical variables, descriptive statistics will include frequency count and percentage. If missing is observed, a “Missing” category will be added without percentage. For shift tables, total rows and columns will not include patients from the “Missing” category except the “Missing” column and row and percentage will be calculated based on evaluable patients. For continuous variables, descriptive statistics are number of patients, mean, median, standard deviation (SD), 25th percentile (Q1), 75th percentile (Q3), minimum, and maximum.

For parameters assessed across multiple visits, by-visit summaries will be presented for planned visits from Table 1 and Table 2.

Minimum and maximum values will be presented to the same decimal precision as the raw values, mean, median, Q1, and Q3 values to one more decimal than the raw values, and the SD to two more decimals than the raw values. All percentages will be presented to one decimal place. All p-values will be presented with 4 decimal places and will be shown as ‘<0.0001’ if the value is smaller than 0.0001.

Relative study day will be provided in data listings. Day 1 is defined as the date of first treatment. Other study days are defined relative to Study Day 1. Relative day is calculated as (date of interest - date of the first treatment + 1) for study days on or after the date of the treatment start, and as (date of interest - date of the first treatment) for study days prior to the date of the treatment start.

Figures will be created to plot the data where it is deemed necessary. All data collected on study in the eCRF will be included in data listings.

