4.2.1. Analysis of Primary Endpoints

4.2.1.1. HI-E Response and MDS assessments

The proportion of patients with HI-E response ≥ 8 weeks within 24 weeks of etavopivat treatment will be analyzed across the pooled strata and within each stratum. Patients will be considered responders if they satisfy HI-E criteria during any continuous ≥ 8 -week treatment interval up to W24D1.

HI-E criteria are defined based on the patient's transfusion history stratum at D1:

NTD: A patient is considered a responder where at least one continuous interval ≥ 8 weeks occurs where all of the following criteria are met:

- Hb is increased by ≥ 1.5 g/dL relative to baseline at 2 or more consecutive visits
- Relapse date (date of first Hb measurement with < 1.5 g/dL change from baseline following the qualifying increase) occurs at least 8-weeks after the first incidence of qualifying Hb increase
- Patient is free of RBC transfusions

LTB: A patient is considered a responder if they are free of RBC transfusions over any continuous 8-week period.

HTB: A patient is considered a responder if they have a $\geq 50\%$ reduction in RBC transfusion burden relative to baseline RBC transfusion burden per 8 weeks over any continuous 8-week period.

Percent reduction in RBC transfusion burden is calculated for all rolling 56-day intervals in the 24-week primary treatment period (i.e. Days 2-57, Days 3-58,..., Days 113-168) as

$$-100 \times \frac{RBC \text{ units transfused in 56 day interval} - \text{Baseline RBC transfusion burden per 8 weeks}}{\text{Baseline RBC transfusion burden per 8 weeks}}$$

The numerator for the response rate will be the total number of responders (summed across all baseline transfusion categories). The denominator will be the number of patients in the EES.

MDS baseline assessment including the score based on Revised International Prognostic Scoring System (IPSS-R) for MDS and MDS response assessment will be presented in data listings.

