5.2. Changes to Planned Analyses

For the purpose to support an abbreviated CSR, a selected set of endpoints are included in this SAP. The following analysis populations and endpoints mentioned in the protocol are not included:

Protocol Section 3.2:

- The HI-E for \geq 8 weeks within 16 and 48 weeks of etavopivat
- The HI-E for \geq 16 weeks within 24 and 48 weeks of etavopivat
- Overall response rate (2006 International Working Group [IWG] Criteria) (see protocol Appendix A)
- Duration of response (2006 IWG Criteria)
- Increase in neutrophils and/or platelets counts
- Decrease in ferritin and transferrin saturation (TSAT)
- Decrease in iron chelation therapy
- Overall survival

Protocol Section 3.3:

- PK: maximum observed plasma concentration, time to maximum observed plasma concentration, area under the plasma concentration-time curve from time zero until the last quantifiable time point (AUC0-last), from time zero to infinity (AUC0-inf), for a dosing interval (AUCtau/AUC0-24).
- RBC 2,3-DPG and ATP levels over time

Protocol Section 3.4:

- Change from baseline in Patient-Reported Outcome Measurement Information System (PROMIS) Fatigue Scale at Weeks 16, 24, and 48
- Change from baseline in The Quality of Life in Myelodysplasia Scale (QUALMS) patient-reported outcome assessment at Weeks 16, 24, and 48
- Cell colony analysis of bone marrow progenitors
- Cytomorphology (blast, M/E, and ringed sideroblast determination) and cytogenetics of bone marrow
- Markers of ineffective erythropoiesis and iron metabolism
- Cancer-associated mutations and/or genetic alterations in responding and non-responding patients
- Flow cytometry analysis of terminal erythroid differentiation

Protocol Section 9.2:

- Interim Assessment Set and Per-Protocol Set

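### Protocol 9.6.1 states the primary hypotheses back to front (the alternative is a response rate below 20%) and on the observed proportion, and the SAP neither corrects nor drops the test

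*Protocol*

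**What the plan says.** Protocol 9.6.1 introduces the primary test with "Analysis of the pooled incidence will test the hypothesis" and then prints H0: 0.2 ≤ P1 and H1: 0.2 > P1. It sets the null proportion P0 at 0.20 and says that P1 "is the observed proportion for etavopivat treated patients. This will be tested using a one-sided binomial exact test at the significance level of 0.025". It does not name the tail. The same section asks for the test within each stratum, and Protocol 9.6.2.1 and 9.6.2.2 apply the same method to the secondary HI-E endpoints.

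The sample-size text points the other way. Protocol 9.3 speaks of "power to detect an increase in the response rate for the HI-E criteria", with assumed rates of 40% on etavopivat and 20% under the null, one-sided 0.025, exact binomial. SAP 3.1 repeats it: "An overall sample size of N=45 will provide 87.3% power to detect an increase in the response rate for the HI-E criteria".

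On the primary endpoint, SAP 4.2.1.1 defines responders and a response rate: "The denominator will be the number of patients in the EES". It gives no hypotheses, null rate, significance level or tail. SAP 5.1 says that nothing needs clarifying. SAP 5.2 opens its list with "The following analysis populations and endpoints mentioned in the protocol are not included", and the primary test is not on the list. SAP 3.2 keeps a reporting format: "All p-values will be presented with 4 decimal places".

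**The concern.** The alternative is what the trial sets out to show. As printed, it is a response rate below 20%, so a one-sided test of the pair rejects when responders are few. That is the opposite of the benefit for which the trial was sized. It also sits badly with Protocol 9.5, where few responses are the sign of failure.

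A second defect stands in the same lines. P1 is defined as the observed proportion. A hypothesis concerns the unknown true probability, because the observed proportion is known once the data are in. This is wrong whichever way the inequalities point.

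Protocol 9.6.1 is the only formal statement of the primary hypothesis in either document. If a p-value is produced from it as written, a clearly positive result would be reported as no evidence at all, and a very poor one as significant. A reader of the SAP also cannot tell whether the test will be run.

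**Working it through.** **Inputs.** N = 45, null rate 0.20, assumed rate 0.40, one-sided 0.025, exact binomial (Protocol 9.3, SAP 3.1). The printed hypotheses come from Protocol 9.6.1. The futility rule of 3 or fewer responses among 15 comes from Protocol 9.5. X is the number of responders.

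**1. Which direction reproduces the plan's power?** In the upper tail, take the smallest r with P(X ≥ r | 45, 0.20) ≤ 0.025:

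- P(X ≥ 14 | 0.20) = 0.0521, too large
- P(X ≥ 15 | 0.20) = 0.02499, so r = 15
- Power: P(X ≥ 15 | 0.40) = 0.8570

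The exact power of 85.7% is 1.6 points below the stated 87.3%. The normal approximation comes closer: Φ[((0.4 − 0.2)√45 − 1.96√0.16)/√0.24] = Φ(1.138) = 0.8725. By either route, the stated power belongs to an upper-tail test.

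**2. The printed pair.** With H1 below 0.20, take the largest k with P(X ≤ k | 45, 0.20) ≤ 0.025:

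- P(X ≤ 4 | 0.20) = 0.0382, too large
- P(X ≤ 3 | 0.20) = 0.0129, so k = 3
- Rejection probability at a true 40%: P(X ≤ 3 | 0.40) = 4.9 × 10⁻⁷

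**3. The same data under each reading.** Suppose 18 of 45 respond (40%):

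| Reading | Rejection region at n = 45 | Exact alpha | P(reject) at true 40% | p-value at 18/45 |
|---|---|---|---|---|
| As printed (H1 below 0.20) | 3 or fewer | 0.0129 | 4.9 × 10⁻⁷ | P(X ≤ 18 \| 0.20) = 0.9994 |
| As intended (H1 above 0.20) | 15 or more | 0.02499 | 0.857 | P(X ≥ 18 \| 0.20) = 0.0017 |

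**4. The futility rule as a check on intent.** P(X ≤ 3 | 15, 0.40) = 0.0905. This matches Protocol 9.5: "Assuming the pooled response rate of 40% is met, the probability of incorrectly declaring futility with 15 evaluable patients is 0.0905". Low counts are treated there as failure, which agrees with the upper-tail reading.

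**5. Dependence on the evaluable number.** The documents do not give the size of the Efficacy Evaluable Set after early termination, so every n below other than 45 is an assumption for illustration.

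| n | Intended cut-off | Exact alpha | Power at 40% |
|---|---|---|---|
| 30 | 12 | 0.0095 | 0.569 |
| 40 | 14 | 0.0194 | 0.789 |
| 45 | 15 | 0.02499 | 0.857 |
| 46 | 16 | 0.0138 | 0.808 |

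**The case against.** The best reply is that nobody would run the test as printed. Protocol 9.6.1 gives the null rate, the level and the exact binomial method, and Protocol 9.3 and SAP 3.1 make the direction plain. No design quantity depends on the two lines. The study has ended early, and the SAP for the abbreviated report asks only for a response proportion and drops the secondary HI-E endpoints. The p-value format in SAP 3.2 sits among general rounding rules and is weak evidence that a primary test is planned. The reference to an observed proportion is loose wording that alters no calculation. The futility rule governs enrolment and does not test against 20%.

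Much of this stands. The intent is recoverable, the error looks like a transposition, and the practical effect is small. The futility rule supports the intended direction and is not a competing hypothesis. An exact test adapts to the actual n, and neither document fixes a cut-off of 15, so the table of cut-offs guides reporting and is not a further fault.

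It does not remove the point. An obvious error in the formal primary hypothesis still needs correcting, because reported results are checked against that statement. Protocol 9.1 leaves changes to the planned analyses to the SAP, and SAP 1.1 undertakes to set out differences from the protocol, yet the SAP is silent on this one. A misread symbol in the text extraction is also an unlikely cause: the two printed lines are exact complements, so both would have had to flip.

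**Conclusion.** The concern holds. The printed alternative is reversed and is written on the wrong quantity, and nothing in either document corrects it. Taken literally at n = 45, it turns a test with 85.7% exact power at a true 40% into one that almost never rejects there (about 4.9 × 10⁻⁷), and it turns p = 0.0017 into p = 0.9994 for 18 responders. These figures assume 45 evaluable patients and independent responses with a common probability.

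This is an error of statement that should be fixed, not a flaw in the design. Sample size, level and futility rule are unaffected. Its importance is reduced by the early termination and the abbreviated analysis. The open question that remains is whether the primary test is to be carried out at all.

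**What to change.** In Protocol 9.6.1, write H0: P1 ≤ 0.20 against H1: P1 > 0.20, define P1 as the true pooled HI-E response probability, and reject when the exact upper-tail binomial p-value is at most 0.025.

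In the SAP, do one of two things:

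- restate this test in 4.2.1.1, with the p-value and any quoted cut-off computed for the actual number in the Efficacy Evaluable Set (15 applies at n = 45 but not, for example, at n = 40 or 46); or
- record in 5.2 that the test is dropped and only the response proportion is reported.

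The cost is two lines in the protocol and one sentence in the SAP. If a protocol amendment is not worthwhile in a terminated study, the SAP sentence should also state the correct direction, and the study report should repeat it.
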